3.8 RANDOMISATION

Participants will be randomised via randomly permuted blocks using an automated web-based system on a one-to-one basis, stratified by site and prior randomisation to another CoReCCT trial, using a computer-generated randomisation schedule managed by the Warwick CTU. We have selected a parallel group RCT design to minimise selection bias and ensure against accidental bias.

3.9 POST-RANDOMISATION WITHDRAWALS, EXCLUSIONS AND MOVES OUT OF REGION

Participants, or their consultee on their behalf, may request to be withdrawn from the trial at any time without prejudice. Those that choose to withdraw from the trial intervention will continue to be followed-up as per the trial protocol, unless consent for this is explicitly withdrawn by the participant (or consultee if the participant lacks capacity).

In the event that a participant is transferred to another hospital, intervention delivery will usually stop at the point of transfer. The recruiting hospital will liaise with the new hospital to facilitate collection of follow-up data.

In the event that a randomised participant is later found to be ineligible, they will continue to be followed-up and will be included in study analyses.

If a NAVA catheter is replaced by a non-NAVA catheter before 28 days based on clinical grounds this will be considered an intervention withdrawal.

3.10 CO-ENROLMENT

The UK NAVA trial investigators will consider co-enrolment to other interventional trials outside of CoReCCT where there are no possible treatment interaction and conflict with the trial objectives. Co-enrolment agreements will be put in place on concurrently running trials. Co-enrolment will be permitted with non-interventional observational studies without the need for a co-enrolment agreement. Co-enrolment status will be collected using the eCRF. Co-enrolment will be managed in line with the approach agreed within the national critical care community.

3.11 MEASURES TO AVOID BIAS

The open-label design of this trial means that patients and clinicians are aware of treatment allocation. Although blinding was considered, during trial design meetings, this is not feasible as clinical teams cannot be blinded to ventilator settings. These and the patient response must be visible to guide clinical decision making and ensure patient safety. While lack of blinding can introduce bias, we have safeguards in place to mitigate against this risk as described below.

To mitigate against potential sources of bias with an open label design, we will:

- undertake source verification (from the electronic (or paper) medical record) to minimise the risk of reporting bias. The main clinical and resource utilisation outcomes of this study (e.g., ventilation duration, death, length of stay and adverse events) are recorded contemporaneously in the patient medical record by a member of the clinical team as part of routine documentation.
- use the duration of ventilation as our primary outcome as this is objectively measured and documented in the medical record. Other secondary outcomes are also objective; only health-related quality of life requires participant self-report.
- use a short duration of follow-up for the primary outcome (i.e., 48 hours to determine successful extubation) to minimise the risk of loss to follow-up and attrition bias. On the rare occasion that a patient or their representative chooses to withdraw, we will seek permission to retain data collected up until that point and to continue to collect the main outcome data. Our experience is that patients or their representatives normally are happy to proceed on this basis.

- monitor usual care in the control arm over the duration of the trial to decrease the likelihood of performance bias. We will feedback monitoring data to sites monthly and provide additional training if required.
- collect measures of intervention fidelity over the duration of the trial and feedback monitoring data to sites monthly. If poor fidelity is found, we will provide additional training and support to sites and continue to monitor fidelity. Sites with ongoing issues with intervention fidelity will be closed to recruitment.

We have selected outcomes and measures with demonstrated validity and reliability recommended in the core outcome set for trials of interventions to modify mechanical ventilation duration developed by members of our team ([name], [name], [name]) [3]. Health-related quality of life will be collected by blinded assessors independent of the clinical team involved in delivering the intervention.

We have used the SPIRIT guidelines and checklist to inform the development of our protocol. We will register the trial and will make a full study protocol publicly available. To ensure our trial reporting is accurate, comprehensive, and transparent, we will use the CONSORT- reporting guidelines to report out study findings. We will document participant flow through the study, including screening, baseline and follow up assessments using a CONSORT flow diagram. To avoid selective reporting, we will report all outcomes as outlined a priori in our study protocol.

We will use Warwick CTU standardised operating procedures for trial conduct.

3.12 SITE STAFF TRAINING

A programme of training will be provided to individuals at hospital sites with responsibility for the assessment of eligibility criteria and randomisation of participants. We will develop web-based training resources that enable site staff to complete training at a time convenient to them. If it is more convenient to specific individuals, training may be provided in person or via video conferencing. This training may be delivered by WCTU staff or by the site principal investigator, or a member of the site team that has been approved to deliver training by the principal investigator. Each hospital site will maintain a training completion log.

We will develop a bespoke training package for clinical members of staff that may be involved in using NAVA technology (See NAVA Technology Training).

4 INTERVENTIONS

4.1 INTERVENTION ARM (NAVA TECHNOLOGY)

We will compare NAVA Technology to conventional IMV. NAVA technology uses a specialised nasogastric/orogastric tube (NAVA catheter) to obtain the electrical activity of the diaphragm (EDi) muscle, which is a reliable index of the patient's respiratory drive. Once the NAVA catheter is placed and connected, the EDi is always visible to clinicians, allowing optimisation of ventilator settings in any mode. When the NAVA mode is active, the ventilator triggers, cycles and adjusts support in synchrony and proportion to the EDi.

There are three components of the UK NAVA trial intervention:

1. EDi signal acquisition and optimisation
2. NAVA monitoring
3. The NAVA mode: proportional and synchronous pressure support, controlled by the EDi signal

Every patient who is randomised to the NAVA Technology arm will receive

1. NAVA catheter insertion
2. Hourly EDi signal monitoring
3. NAVA mode ventilation for weaning

DRAFT

[figure not shown]

Figure 2. NAVA system components: EDi Module (1) EDi Cable (2) EDi Test Plug (3) NAVA NGT (4). Adapted from NAVA User's Manual. Maquet Servo-i® ventilator system version 4.0. Maquet (Solna, Sweden).

4.1.1 COMPONENT 1: EDI SIGNAL ACQUISITION AND OPTIMISATION

4.1.1.1 NAVA NGT INSERTION

1. Select NAVA catheter:
2. 16 French: Patient height >140 cm (>55.1 in) French
3. 12 French: Patient height 75 to 160 cm (29.5 to 63.0 in) Connect the EDi module and cable
4. Perform the EDi module function check
5. Measure the NEX distance in cm
6. Determine the insertion distance (use tape measure or on-screen calculator)
7. Dip the NAVA catheter in water and insert. Do not use silicone spray or other lubricants as the NAVA catheter is pre-lubricated. This may result in the NAVA catheter malfunctioning (Tip: cover with water while in the clear plastic tray packaging)
8. Connect the NAVA catheter to the ventilator via the EDi cable
9. Verify the position in the positioning window (**Figure 3**)
10. Secure the NAVA catheter to the patient
11. Document insertion distance
12. Check position for enteral feeding according to local policy, e.g., X-ray, pH
13. Correct positioning using the positioning window should be verified every 12 hours

Note 1: There is no procedural difference with placing and feeding via a NAVA catheter versus a regular NGT feeding catheter. Placement should be performed by trained clinicians according to local guidelines. The ventilator positioning window / positioning tool must NEVER be used to confirm gastric position prior to feeding

Note 2: NAVA catheters may be used for **five** consecutive days. After this time, catheters should be removed and replaced. See section 6.7 'NAVA Technology Intervention Duration' for further detail.

Note 3: NAVA catheters contain metal and are not approved for use in MRI environments. Catheters should be removed prior to MRI scanning. Catheters that are removed may be retained and replaced.

4.1.1.2 EDI OPTIMISATION (ERROR! REFERENCE SOURCE NOT FOUND.)

1. Open the NAVA catheter positioning window
2. Perform interventions to promote inspiratory effort if necessary *
3. Make adjustments to the NAVA catheter position (insertion depth) to obtain the optimum diaphragmatic signal:
 - a. Pink/blue highlighted second and third leads
 - b. Descending signal amplitude
 - c. EDi signal is present

* Patients may be switched from mandatory ventilation modes to PSV, NAVA or CPAP mode in order to promote spontaneous breathing.

[figure not shown]

Figure 3. Correct NAVA NGT position, indicated by pink/blue highlights in the middle two leads, and a descending signal amplitude from top to bottom

Other suggested interventions include sedation reduction, ventilation support reduction, or expiratory breath hold.

4.1.2 COMPONENT 2: NAVA MONITORING

Electrical diaphragmatic activity (EDi) is displayed on the ventilator screen as a dynamic curve and as stored trend data. The EDi peak represents maximal electrical activity of the diaphragm for a particular breath (measured in μV). The EDi min represents the electrical activity of the diaphragm between inspiratory efforts (measured in μV). This information may be used to optimise ventilator settings and sedation in any mode. In addition to usual ventilator observations, the following should be performed/recorded by clinical staff

1. EDi optimisation check/adjustment as above, every 12 hours (must be recorded)
2. EDi trend check, daily/as required
3. EDi observations, hourly (the maximum EDi must be recorded)

4.1.3 COMPONENT 3: THE NAVA MODE

The NAVA mode should be commenced during the weaning phase once the patient is able to trigger $\geq 50\%$ of ventilator breaths, and a stable EDi signal has been acquired and optimised (see above). The NAVA level (set by the clinician on the ventilator) is the amplification factor by which the EDi signal is multiplied to determine the level of assist to the patient (in cmH_2O). The maximum pressure assist provided during a breath is: Peak pressure (cmH_2O) = NAVA level \times (EDi peak – EDi min) + PEEP. For example, if NAVA level is set to $1 \text{ cmH}_2\text{O}/\mu\text{V}$ with a peak EDi for a specific breath of $10 \mu\text{V}$, the maximum level of support delivered for that breath is $10 \text{ cmH}_2\text{O}$. As with all modes, the maximal pressure will be limited to 10% below the set limit within the 'alarms' settings.

4.1.3.1 NAVA MODE PREPARATION

1. To determine starting NAVA level, either:
 - a. Select NAVA level $1.0 \text{ cmH}_2\text{O}/\mu\text{V}$, **OR**
2. Use the preview window to estimate the same or just below positive inspiratory pressure as delivered in the previous mode
3. Set back-up ventilation
4. Optimise the diaphragmatic EDi signal (minimise sedation)

4.1.3.2 AFTER COMMENCEMENT: TITRATING AND OPTIMISING THE NAVA MODE

1. Titrate the NAVA level with the same principles used to titrate pressure support according to
 - a. Tidal volume, aiming for $6\text{--}8\text{ml/kg}$ predicted body weight
 - b. Respiratory rate
 - c. A visual assessment of breathing and patient comfort
2. Monitor for cardiovascular stability, desaturation, increased work of breathing, or tachypnea

4.1.4 NAVA TECHNOLOGY TRAINING

All site staff will complete a training package appropriate to their role prior to opening to recruitment. The training package will include information on set up, optimisation, and weaning of the NAVA mode; trouble shooting guides; and a review of standard of care approaches for the management of ventilator weaning.

4.2 CONTROL ARM

Ventilation in the control arm will follow current best practice within the participating centres adhering to conventional lung protective ventilation. Any non-automated mode of ventilation can be used.

4.3 BOTH GROUPS

4.3.1 VENTILATOR WEANING

Weaning will be conducted according to the usual practices of the participating site (low level support, stepwise reductions, periods of CPAP or T-Piece) and may or may not include a spontaneous breathing trial. In general, criteria for readiness to wean as presented in the recent Weansafe international observational weaning trial (Lancet Respiratory, May 2023), comprise the following:

1. $FiO_2 \leq 40\%$, $PEEP \leq 8$ cmH₂O
2. Systolic blood pressure > 90 mmHg
3. Vasoactive drugs reduced or unchanged over previous 24 h
4. Patient has acceptable breathing efforts
5. Improvement in underlying condition and no requirement for controlled ventilation

4.3.2 STANDARD INDICATIONS TO INCREASE VENTILATION SUPPORT DURING WEANING

1. Increased anxiety
2. Reduced SpO₂ saturation ($<88\%$ or a drop of $>5\%$)
3. Significant heart rate change or acute cardiac dysrhythmia
4. Signs of respiratory distress, including tachypnoea or new use of accessory muscles

4.3.3 EXTUBATION

The decision to extubate will be that of the individual clinicians based on local experience and patient response

4.3.4 OTHER CLINICAL MANAGEMENT

Responsibility for all other management decisions remains the responsibility of the attending physicians and ICU team. Measures such as prone positioning, continuous neuromuscular blockade infusion, inhaled pulmonary vasodilators, or referral for consideration of extracorporeal membrane oxygenation (ECMO) can be applied in either arm of the trial as per standard care in the UK.

4.4 INTERVENTION DURATION

The intervention (NAVA technology or control) will continue until one of the following criteria is met:

- 28 days after randomisation
- Successful unassisted breathing
- Study intervention-related serious adverse event
- Death or discontinuation of active treatment
- Person giving consent requests discontinuation of intervention
- NAVA equipment unavailable

NAVA catheters are currently licensed for a maximum of five days' use. Where it is clinically appropriate and safe, NAVA catheters should be replaced at five days. Use of individual NAVA catheters for more than 5 days is outside the trial protocol. Although this will not be reported as a protocol deviation, the clinical justification will be recorded.

4.5 INTERVENTION ADHERENCE AND CROSSOVER

Each day, we will record the ventilator settings for participants. The statistical analysis plan will define adherence to the trial intervention.

As a minimum requirement, intervention arm patients must receive a NAVA catheter. Control arm patients must not receive a NAVA catheter. Cross-over will not be allowed. This will be monitored during the trial. If any site despite re-training continues to experience cross-over, the site will be closed to recruitment.

5 ASSESSMENTS AND DATA COLLECTION

Data collection will be restricted to variables required to define patient characteristics at enrolment, to monitor interventions received, to monitor adverse effects, to determine health-related quality of life after hospital discharge, to capture the use of hospital healthcare resource and healthcare resource utilisation after hospital discharge. To ensure accurate, complete and reliable data are collected, the research team will provide training to site staff during investigator meetings and site initiation visits. The CTU will provide the PI and research staff with training on the protocol, CRF completion and trial procedures including standard operating procedures (SOPs).

Core baseline variables will be collected once and shared across the relevant domains of CoReCCT. These, and other data management details can be found in sections 6 and 10 of the CoReCCT master protocol. In addition to the core dataset, items related to the NAVA-specific outcomes will be collected.

5.1 TRIAL PROCEDURES SCHEDULE

Table 4. Data collection schedule

	Baseline	Up to ICU dx	Up to hospital dx	2 months	6 months
Screening for eligibility	X				
Informed consent	X				
Baseline data collection	X				
Randomisation	X				
Ventilator settings, sedation use, organ failure		X			
Adverse events		X	X		
Primary & secondary outcomes		X			

Mortality (secondary outcome)		X	X	X	X
HrQoL (secondary outcome)				X	X
Healthcare utilisation after dx				X	X

5.2 FOLLOW UP PROCEDURES

Full details on follow up data collection procedures can be found in Section 6.5 of the CoReCCT master protocol.

6 SAFETY AND ADVERSE EVENTS

In order to accurately assess and report SAEs relevant to RELEASE, the CoReCCT Master Protocol must be read in conjunction with section 4.1 below. Section 7 of the CoReCCT Master Protocol describes the CoReCCT Safety Reporting Flowchart and provides details on these adverse event management topics:

- Definitions of SAEs
- Assessing and reporting SAEs
- Causality Assessment of SAEs
- Expectedness Assessment of Related SAEs
- Expedited Reporting of Related and Unexpected SAEs to REC

6.1 PRE-SPECIFIED COMPLICATIONS

As per the CoReCCT Safety Reporting Process (Section 7 of the CoReCCT Master Protocol), adverse events that 1) occur at sites between randomisation and hospital discharge and 2) are not present on the CoReCCT Exemption List, must be reviewed for their presence on the NAVA Pre-Specified Complications List as given below:

- Related to naso-gastric catheter placement;
 - a. Naso-gastric tube entering brain
 - b. Naso-gastric tube positioned in lungs (unrecognised/not corrected)
 - c. Traumatic nasogastric catheter insertion (oesophageal perforation)
 - d. Traumatic nasogastric catheter insertion (nasal/pharyngeal bleeding)
 - e. Aspiration of stomach contents
 - f. Pneumothorax
- Other
 - a. Unplanned removal of ETT or Tracheostomy
 - b. Unplanned removal of naso-gastric tube
 - c. Unplanned removal of any other invasive/indwelling device
 - d. Any pressure injury caused by naso-gastric catheter
 - e. MRI scan performed with NAVA naso-gastric catheter in situ (NAVA catheters are MRI unsafe due to potential harm from movement or the generation of heat in the metallic electrodes. They may also cause artifacts in the MRI images.)

The events listed above must be entered onto the eCRF when appropriate as outcomes of interest, and therefore are exempt from SAE reporting. If an event occurs which does not appear either on the

CoReCCT Exemption List or on the NAVA pre-specified complication list above, it must be assessed for seriousness, and the remainder of the CoReCCT safety reporting process should be followed to determine the next steps to be taken. Pre-specified complications will be collected onto the eCRF for the duration of the trial intervention up to 28 days. Any occurrence following this will be reported via the safety reporting process described in Section 7 of the CoReCCT Master Protocol.

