1 TRIAL SUMMARY

Table 1. Trial summary

Master protocol title	CoReCCT - Confederation of Respiratory Critical Care Trials
Domain protocol title	Neurally Adjusted Ventilatory Assist (NAVA) Technology (diaphragm monitor and NAVA mode) vs conventional invasive mechanical ventilation (IMV) for patients at risk of difficult or prolonged weaning from IMV: The UK NAVA Trial
Short title/acronym	UK NAVA
Clinical phase	Phase 3 effectiveness & cost-effectiveness
Purpose of research	To investigate, using a multi-centre, parallel group, pragmatic, randomised controlled trial design, the clinical and cost effectiveness of Neurally Adjusted Ventilatory Assist (NAVA) compared to conventional IMV in adult patients with risk factors for difficult or prolonged weaning from IMV treatment
Trial design	Parallel group randomised controlled trial with internal pilot and cost effectiveness analysis
Participants	Adult ICU patients who are at risk of difficult or prolonged weaning from IMV
Planned sample size	900
Treatment duration	≤28 days
Follow-up duration	6 months following randomisation
Planned trial period	May 1 st 2024 to 31 st September 2028
Inclusion criteria	
 1. Age 18 years or over 2. Receiving invasive mechanical ventilation 3. Expected to stay on IMV for ≥48hrs 4. Any clinical risk factor for difficult or prolonged weaning from IMV
Intervention	NAVA technology uses a specialised nasogastric/orogastric tube (NAVA catheter) to obtain the electrical activity of the diaphragm (EDi) muscle, which is a reliable index of the patient's respiratory drive. Once the NAVA catheter is placed, the EDi is always visible to clinicians, allowing optimisation of ventilator settings in any mode. When the NAVA mode is active, the ventilator triggers, cycles and adjusts support in synchrony and proportion to the EDi.
Control	Conventional invasive ventilator modes (no NAVA Technology)
Primary outcome	Duration of mechanical ventilation (time from randomisation to first successful unassisted breathing or death)
Secondary outcomes	
 1. All-cause mortality at hospital discharge, 2 months and 6 months after randomisation 2. Time to first extubation

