3.4.2 SECONDARY OBJECTIVES AND OUTCOMES

Our secondary objectives are to determine the effect of NAVA technology compared to conventional IMV on the following:

- All-cause mortality (2 months and 6 months from randomisation)
- Time to first extubation
- Reintubation
- Use of non-invasive ventilation following extubation
- ICU and hospital length of stay
- Serious adverse events up to hospital discharge
- HRQoL at 2 months and 6 months from randomisation
- Acute health care use at 6 months following randomisation
- Within-trial cost-utility analysis from an NHS hospital care perspective (see below)

- Safety endpoints (see also section 'Serious adverse events up to hospital discharge')
- Pre-specified complications including
 - Naso-gastric tube entering brain
 - Naso-gastric tube positioned in lungs (unrecognised/not corrected)
 - Traumatic nasogastric catheter insertion (oesophageal perforation)
 - Traumatic nasogastric catheter insertion (nasal/pharyngeal bleeding)
 - Aspiration of stomach contents
 - Pneumothorax
 - Unplanned removal of ETT or Tracheostomy
 - Unplanned removal of naso-gastric tube
 - Unplanned removal of any other invasive/indwelling device
 - Any pressure injury caused by naso-gastric catheter
 - MRI scan performed with NAVA naso-gastric catheter in situ
 - Reportable safety events that fall outside of those reported as trial outcomes

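### The insertion-bleeding complication names only nose and pharynx, although the protocol also permits oral placement of the NAVA catheter

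*Protocol*

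**What the plan says.** **Route.** The intervention entry in the trial summary (Protocol, section 1) states: "NAVA technology uses a specialised nasogastric/orogastric tube (NAVA catheter) to obtain the electrical activity of the diaphragm (EDi) muscle". Section 4.1 repeats this definition. The exclusion criteria (3.5.2) consider contraindications to either kind of tube, and the consent section (3.7) also names both.

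**Complication list.** Sections 3.4.2 and 6.1 carry the same 11 pre-specified complications. In 6.1 the first group is headed "Related to naso-gastric catheter placement". The bleeding item is "Traumatic nasogastric catheter insertion (nasal/pharyngeal bleeding", and the pressure-injury item is "Any pressure injury caused by naso-gastric catheter". No item names an oro-gastric tube or a site in the mouth.

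**How the list is used.** Section 6.1 says: "The events listed above must be entered onto the eCRF when appropriate as outcomes of interest, and therefore are exempt from SAE reporting". For an event on neither this list nor the CoReCCT Exemption List, the instruction is that "it must be assessed for seriousness". Section 3.4.2 places the complications among the safety endpoints. It introduces them as a non-exhaustive list and closes with a bullet for reportable safety events not already reported as trial outcomes.

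**The concern.** The list works as a sorting rule. A listed event becomes an eCRF outcome of interest, whether or not it is serious. An unlisted event is assessed for seriousness, and this protocol states no eCRF item for it if it is not serious. What the list names therefore decides whether a minor event is counted in a stated safety endpoint.

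Every patient in the intervention arm must receive a NAVA catheter (4.5). Catheters should be replaced at five days where that is appropriate and safe, and the intervention can last up to 28 days (4.4), so one patient may have several insertions. A minor insertion injury should count the same whichever permitted route was used. As worded, the bleeding item covers the nose for one route but not the mouth for the other.

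**Working it through.** No arithmetic beyond a count applies. The check sets the route wording beside each listed item.

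**Step 1: permitted routes.** Sections 1, 3.5.2, 3.7 and 4.1 each name both the nasal and the oral route.

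**Step 2: classify the 11 items in 6.1.**

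| Group | Items | Number |
|---|---|---|
| Minor oral-route events could be left out | insertion bleeding; pressure injury | 2 |
| Only the reporting channel could change | oesophageal perforation; unrecognised lung position | 2 |
| Worded naso-gastric, but no gap counted | tube entering brain; unplanned tube removal; MRI with catheter in place | 3 |
| No route named | aspiration; pneumothorax; removal of ETT or tracheostomy; removal of another device | 4 |

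Total: 2 + 2 + 3 + 4 = 11.

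In the third group, no oral-route gap is claimed for brain entry. Removal of an oral tube would fall under "Unplanned removal of any other invasive/indwelling device". The MRI item's own explanation speaks of the device generally: "NAVA catheters are MRI unsafe due to potential harm from movement".

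**Step 3: apply two readings.**

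- *Naso-gastric as a generic device name.* Pressure injury, perforation and lung position are then all covered for an oral catheter. Bleeding is not fully covered, because that item is also limited by anatomical site. Pharyngeal bleeding is in; bleeding confined to the mouth is out. Items with a gap: 1 of 11.
- *Naso-gastric taken literally.* The first two groups are affected, 2 + 2 = 4 of 11. In two of these, minor events could be left out (mouth bleeding; lip or mouth pressure injury). In the other two, the event would be assessed for seriousness and follow the safety reporting process instead of being entered as an SAE-exempt outcome, so nothing is lost.

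**Step 4: trace one event.** Take non-serious bleeding confined to the mouth after oral insertion, and assume that it is not on the CoReCCT Exemption List. It is compared with the NAVA list and does not match the bleeding item on either reading. It is then assessed for seriousness and found not serious. The protocol states no eCRF item for it at that point. Had it been serious, it would have continued through the CoReCCT safety process.

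**The case against.** The strongest reply is that naso-gastric is simply what this protocol calls the device. The heading of 4.1.1.1 and the captions of Figures 2 and 3 use NGT for a catheter that 4.1 defines as nasal or oral, and the MRI item treats the two terms as the same. This stands. It makes the generic reading the more likely one and removes most of the problem. The pressure-injury item also has no limit by site, so on that reading lip and mouth injuries are included.

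Second, the list in 3.4.2 is not closed, and its last bullet keeps reportable events among the safety endpoints. This also stands, and it limits the gap further. It does not clearly settle minor mouth bleeding: reportable may mean serious events only, and 6.1 treats the list as the one to check events against.

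Third, the Exemption List, the master protocol's safety section, the working instructions and the eCRF labels are not at hand and may already settle the route. It therefore cannot be said that such events go uncollected, only that this protocol does not list them.

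A reader might infer that oral-route device injuries in general drop out of the safety data, or that the comparison between arms is biased. The documents support neither. The first needs the literal reading throughout and ignores the assessment of unlisted events for seriousness. The second needs the share of oral placement and the complication risk by arm, which the protocol does not give.

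**Conclusion.** The point holds in a narrow form. The bleeding item is limited to nasal and pharyngeal sites, so non-serious bleeding confined to the mouth after a permitted oral insertion is not a listed outcome on either reading. The naso-gastric wording elsewhere is probably generic. It could cause inconsistent recording across the roughly 40 ICUs only if some of them read it literally.

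No event count can be estimated, and the effect on the comparison between arms is unknown in size and direction. Sample size, power and the primary analysis are untouched. The conclusion assumes that the eCRF labels and working instructions follow the protocol wording; if they already name the mouth, only the protocol text needs tidying. Minor: a cheap improvement to a device-safety endpoint.

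**What to change.** In both 3.4.2 and 6.1:

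- Change the sites in the bleeding item to *nasal/oral/pharyngeal bleeding*.
- Write *naso- or oro-gastric* for the tube items, and in the placement heading of 6.1, applied in the same way in both arms.
- Match the eCRF labels, and check now whether they already cover the oral route.

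The cost is a wording change to two lists and one heading, plus the matching eCRF labels. The downside is a slightly higher recorded count of minor complications.
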